9.1. Sample size and statistical power

We will recruit 400 LTBI contacts of active pulmonary TB cases to address the primary objective. This sample size is derived from estimated progression from LTBI to active TB within 2 years of 5%, giving 20 progressors and 380 non-progressors. Progressive disease may be due to a range of different immune responses, and each variation may only be evident in a subset of cases. Therefore, conventional differential gene expression analysis in the TST between groups of progressors and non-progressors, may not identify statistically significant differences. Instead, we will undertake supervised outlier profile analysis to identify gene expression among subsets of progressors, which lies outside the normal range measured in non-progressors. These methods provide robust statistical confidence by incorporating multiple testing corrections³²⁻³⁶, and have been successfully applied to discovery of novel oncogenic pathways^{32,37}. Using preliminary TST transcriptomic data from HIV negative individuals in computational simulations, we estimate >0.8 statistical power in this sample size to detect significant outlier traits among progressors (false discovery rate <0.05) when the outlier trait is shared by 5 or more progressors (Figure 2A). In order to identify eQTLs of TST transcriptomic data, we estimate that a sample size of 1000 is required to give >90% power to detect statistically significant correlations ($p < 10^{-8}$) for allelic frequencies $\geq 5\%$ depending on the correlation coefficients, as a composite measure of effect size and variance⁶¹. Finally, from our pilot data, we estimate that 15% of these individuals will express the blood transcriptional biomarker at time of recruitment to the study. Of these estimated 150 participants, 80 will be recruited to the LTBI treatment sub-study. Conservatively assuming that only 25% of patients decline LTBI therapy, a sample size of 68 participants will provide 80% power to detect a difference of 0.8 standard deviations (SDs) in signature scores between those who accept and decline treatment at each time point. This calculation assumes similar standard deviations among individuals in both groups. We have estimated 0.8SDs as the minimum difference in signature scores that is likely to be of clinical significance (based on the difference in mean scores between IGRA-positive and IGRA-negative TB case-contacts in our pilot data. To allow for losses to follow-up, 80 participants will be recruited.

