
9.2. Experimental approaches and data analysis

Bioinformatic pathway enrichment analysis of outlier gene expression amongst all progressors will be used to identify common immune correlates of risk of progression to active TB at the systems level. To complement this approach, we will also reduce the dimensions of data in the TST transcriptome of all non-progressors, from individual genes into co-correlated clusters as a surrogate for immune networks³⁸. We will compare the expression of each cluster to identify statistically significant differences between progressors and non-progressors. We will then undertake pathway analysis of each differentially expressed cluster to identify the immune pathways that may influence risk of progression to active TB. Data from participants in the cross-sectional study, and those in the longitudinal study who withdraw from the study or are lost to follow up before completing 2 years follow up will be included by identifying any progressors amongst these groups by linkage to national TB surveillance records, held at Public Health England.

All 1000 participants undergoing TST transcriptional profiling will be genotyped for >1.7 million genome wide SNPs using the Illumina Infinium Multi-Ethnic Global-8 array, with additional imputation of >4 million SNPs to allow fine mapping of associations. Statistically significant SNP associations with quantitative variation in the TST transcriptome will be identified as previously described⁵⁷. Iterative eQTL analyses will be performed in year 3 after the first 400 recruits, in year 4 after 750 recruits and in year 5, using data from all 1000 individuals. In addition, we will assess whether any eQTLs are associated with immune response variation that correlate with progression to active TB, thereby identifying potential genotypic susceptibility loci via their association with a functional impact on anti-Mtb immune responses. Where possible, we will assess whether the eQTLs identified in the present study represent significant susceptibility loci for active TB using a targeted (statistically more powerful) analysis approach to re-examine previously published GWAS data. In order to make maximum use of the novel data, we will also identify eQTLs which coincide with loci associated with any phenotypic/disease traits in GWAS catalogues (www.genome.gov/gwastudies/), thereby offering novel mechanistic insights into the associations.

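### Protocol 9.2 infers mechanism from eQTLs that coincide with GWAS-catalogue loci, without a shared-variant test or a chance benchmark

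*Protocol*

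**What the plan says.** The step comes after the main eQTL analyses in section 9.2 and is introduced as an extra: "In order to make maximum use of the novel data". It is described in one sentence: "we will also identify eQTLs which coincide with loci associated with any phenotypic/disease traits in GWAS catalogues", "thereby offering novel mechanistic insights into the associations". The search covers "any phenotypic/disease traits in GWAS catalogues", so it is not limited to tuberculosis or immune traits. No window, linkage-disequilibrium (LD) threshold, same-SNP requirement, joint test or reference overlap is stated.

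Three other parts of the plan bear on it:

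- Participants are "genotyped for >1.7 million genome wide SNPs using the Illumina Infinium Multi-Ethnic Global-8 array, with additional imputation of >4 million SNPs", the imputation being intended "to allow fine mapping of associations".
- The preceding sentence of 9.2 gives tuberculosis susceptibility its own targeted re-examination of published GWAS data.
- Section 9.1 bases eQTL power on 1000 participants at p < 10^-8.

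**The concern.** The sentence contains both a rule and a conclusion, and the conclusion rests on the rule alone. Two association signals can occupy the same locus because one variant drives both, or because two different variants lie close together or in LD. Coincidence at a locus is compatible with either explanation, but only the first says anything about mechanism. Because the search runs over every catalogued trait, some overlaps would be expected even if no eQTL shared a variant with any trait. Without a benchmark, the reader of the results cannot tell how many overlaps exceed that expectation.

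At stake is the interpretation of this secondary use of the data: a list of overlaps could be presented as biological explanation when part of it, possibly a large part, reflects proximity.

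**Working it through.** **Plan's own figure.** The protocol states none for this step, so there is nothing to reproduce.

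**Does another part of the plan supply the missing test?**

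- Fine mapping localises the study's own associations. No joint analysis with the external GWAS signal is described.
- The targeted re-examination of GWAS data concerns active tuberculosis only. The any-trait search has no counterpart.
- The p < 10^-8 level limits false eQTLs. It does nothing about a true eQTL that lies near an unrelated GWAS locus.
- The in vitro work in 9.2 validates eQTL associations and examines Mtb growth. It does not test links to catalogue traits.

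None of the four asks whether an eQTL and a catalogue trait share a variant.

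**Size of chance overlap with a positional window.** The inputs are assumptions, because the protocol gives none of them: genome G = 3,000 Mb; L independent catalogue loci, 1,000 to 10,000; half-window w, ±50 to ±250 kb; m eQTLs; uniform and independent positions.

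Per eQTL: p = 1 − exp(−L × 2w / G).

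At least one of m: P = 1 − (1 − p)^m.

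| L | w | p per eQTL | P, m = 10 | P, m = 100 |
|---|---|---|---|---|
| 1,000 | 50 kb | 1 − exp(−1000 × 0.1/3000) = 0.033 | 0.28 | 0.96 |
| 3,000 | 100 kb | 1 − exp(−3000 × 0.2/3000) = 0.181 | 0.86 | ~1.00 |
| 10,000 | 250 kb | 1 − exp(−10000 × 0.5/3000) = 0.811 | ~1.00 | ~1.00 |

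Among 100 eQTLs the expected number of chance overlaps is 100p, or about 3 to 81.

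**Narrower rules.**

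- ±10 kb with L = 1,000: p = 1 − exp(−1000 × 0.02/3000) = 0.0066. P is about 6% for 10 eQTLs and 49% for 100.
- Same-SNP match: p = L/M, with M = 1.7 + 4 = 5.7 million SNPs (the protocol's two lower bounds added). L = 1,000 gives 1,000/5,700,000 = 0.02%. L = 30,000, a more generous catalogue than in the table, gives 0.5%. P runs from 2% to 41% for 100 eQTLs and from 16% to 99.5% for 1,000.

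The per-eQTL chance therefore runs from about 0.02% to 81% over these cases. The matching rule is the main driver: at L = 1,000 alone, moving from a same-SNP match to ±250 kb takes p from 0.02% to 15%. Uniform placement probably understates the windowed figures, because eQTLs and GWAS hits both cluster near genes.

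**The case against.** The strongest reply is that the word used for matching is undefined, not wrong. It could cover a same-variant match, an LD criterion or formal colocalisation, and the operational rule for an exploratory look-up is the kind of detail a statistical analysis plan may hold. Every numerical input above is assumed. The step is not among the objectives in 3.1 and 3.2, and no sample size depends on it. Recall for the mechanistic experiments uses other criteria.

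Much of this stands. A reader might infer that chance matches will affect many eQTLs, that the set will almost always contain one, or that the rule returns hits whatever the truth. The documents do not support those readings: the lowest windowed case is 3% per eQTL and 28% for at least one of 10, and a same-SNP rule is far lower. A reader might also infer that the plan makes formal disease claims from overlap. It does not; it promises insights. Nor are the 5.7 million SNPs the size of this search, since the catalogue is consulted for identified eQTLs.

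What does not stand is that detail elsewhere would settle the matter. The protocol itself derives the insight from coincidence, and defining a window would leave that inference resting on position. A same-SNP match helps with chance, but one SNP can still tag two different causal variants.

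**Conclusion.** The point holds in a limited form. As written, 9.2 draws mechanistic insight from coincidence with a locus, and nothing else in the protocol tests for a shared causal variant or gives the overlap expected by chance. That inference is unsound whatever the catalogue size.

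The numerical size is conditional. Under a windowed rule with the assumed 1,000 to 10,000 loci and ±50 to ±250 kb, at least one chance overlap is likely to near certain once the eQTL set reaches 100. Under a strict same-SNP rule or with a small eQTL set it need not be. The protocol does not say which rule applies. The consequence is confined to an exploratory add-on: the primary objective, the listed secondary objectives and the sample sizes are unaffected. This is a worthwhile improvement, not a flaw in the study's main analyses.

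**What to change.** Amend the sentence in 9.2 so that:

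1. For eQTL-trait pairs with summary statistics, a mechanistic statement requires evidence of a shared causal variant. This can be a prespecified colocalisation posterior threshold (0.8, for example) or loss of the eQTL signal after conditioning on the GWAS lead SNP.
2. The number of overlaps is compared with the number found for control SNPs matched on allele frequency, LD and distance to gene.
3. Overlaps based on position only are reported as a descriptive list, without a mechanistic claim.

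The criterion should be fixed before results are seen, because 9.2 repeats the eQTL analysis after 400, 750 and 1000 recruits and the matching rule could otherwise be chosen afterwards.

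The cost is protocol or analysis-plan wording and computing time; no extra participants, samples or visits are needed. The downside is that traits without public summary statistics remain descriptive.

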12.1. Data outputs

A case record form (CRF, Appendix 10) will be completed for each study participant. The CRF will be the only document with participant identifiable data. The CRF's will be kept in the study master file which will be stored in secure UCL offices with restricted access under the custodianship of the Chief Investigator. All study data will be linked to the participant UIN only without any participant identifiers. This project will generate 1000 genome-wide transcriptional profiles of the in vivo human immune response to the tuberculin test, using RNA sequencing at a depth of 20-30 million reads, as a model for in situ host-pathogen interactions in tuberculosis as well as a prototypic model of cell mediated immune responses in general. 1000 SNP genotype profiles will also become available from the same individuals using the most comprehensive multi-ethnic SNP array currently available. In addition a subset of 400 individuals within this cohort will generate longitudinal data on blood transcriptomic biomarkers of active TB data combined with high resolution clinical metadata. We will also seek to share anonymised linked clinical metadata. Each data set and the combination of linked data will be of exceptional value to discovery science in tuberculosis specifically and infection/immunology research more broadly, as well to the translational applications of blood transcriptional profiling. Data analysis will be conducted by designated research staff under the supervision of the chief investigator. Specific analysis will include the transfer of anonymised electronic data to designated collaborators under the terms of data transfer agreements, in which collaborating partners will be responsible for restricting use of the data to agreed purposes, maintenance of confidentiality and data security, reporting publications and other outputs to the CI of this study and restricting onward transfer of samples to a third party.

12.2. Data sharing

The data will be made available at the time of peer-reviewed publications, or by 12 months after completion of the project. Raw transcriptomic, genotyping data and linked phenotypic data will be made available through quality controlled public repositories to maximise their use by the scientific community. Specifically, European Bioinformatics Institute Array Express repository (<http://www.ebi.ac.uk/arrayexpress>), for genome-wide transcriptomic data, and the European Bioinformatics Institute Genome-Phenome archive (<https://www.ebi.ac.uk/ega>) for genotypic and phenotypic data. Processed/analysed data sets will also be made available through supplementary on-line content associated with peer-reviewed scientific publications.

Potential users of the research data will be able to find out about our data through peer reviewed research publications, presentations at seminars or international conferences in the field of study and through institutional press releases where appropriate. Accession numbers to our data within public repositories will be provided in research papers and identifiable through conventional search facilities provided by each facility.

The terms of participant consent, restrictions resulting from intellectual property rights and prior collaborations or the lack of good quality metadata are all potential restrictions to data sharing. Specifically, we will not share any data from which individual patients can be identified directly or through association with other data sources.

12.3. Data security and governance

We will minimise risk of deficiencies in data collection and storage. We will obtain specific consent from participants to include provision for data sharing. All electronic data will be stored in password encrypted computer facilities, maintained by information technology services within the Division of Infection & Immunity at UCL, and backed up by automated synchronisation within dedicated divisional servers with password protected access. Paper records will be kept in locked research offices within the Division of Infection & Immunity at UCL, within research buildings subject to secure electronic card or code access. All processes and events related to the projected will be logged in laboratory records, including provenance of data, their coding and detailed descriptions for variables. Personal identification information will be restricted to the study master file in hard copy and password encrypted electronic database, annotated with UIN codes to link to experimental data. Instrument metadata will be collected in curated electronic archives, annotated with relevant information for each experiment including UIN for specific experiments and study participants. All procedural and data analysis protocols (including amendments) will be stored as curated electronic files. At the end of the study, data will be fully anonymised by unlinking the UIN from identification information for each participant. Long-term storage will be undertaken in the UCL digital data repository (<http://www.ucl.ac.uk/library/digital-collections>) as well as the public repositories specified above.

12.4. Document archiving

UCL and each participating site recognise that there is an obligation to archive study-related documents at the end of the study. The CI confirms that he/she will archive the study master file through the UCL Library Records Office (<http://www.ucl.ac.uk/library/about/records-office>) for 25 years and in line with all relevant legal and statutory requirements. The Principal Investigator at each participating site agrees to archive the respective site's study documents for 25 years and in line with all relevant legal and statutory requirements.

12.5. Intellectual property

All background intellectual property rights (including licences) and know-how used in connection with the study shall remain the property of the party introducing the same and the exercise of such rights for purposes of the study shall not infringe any third party's rights.

All intellectual property rights and know-how in the protocol and in the results arising directly from the study, but excluding all improvements thereto or clinical procedures developed or used by each participating site, shall belong to UCL. Each participating site agrees that by giving approval to conduct the study at its respective site, it is also agreeing to effectively assign all such intellectual property rights (IPR) to UCL, and to disclose all such know-how to UCL.

Each participating site agrees to, at the request and expense of UCL, execute all such documents and do all acts necessary to fully vest the IPR in UCL.

Nothing in this section shall be construed so as to prevent or hinder the participating site from using know-how gained during the performance of the study in the furtherance of its normal activities of providing or commissioning clinical services, teaching and research to the extent that such use does not result in the disclosure or misuse of confidential information or the infringement of an intellectual property right of UCL. This does not permit the disclosure of any of the results of the study, all of which remain confidential.

Intellectual property protection will be undertaken through collaboration with UCL Business (<http://www.uclb.com/>).

13. Funding

The study funding has been reviewed by the UCL/UCLH Research Office, and deemed sufficient to cover the requirements of the study. NHS costs will be supported via UCLH and/or the Local Clinical Research Network.

The research costs for the study have been supported by a Wellcome Trust Investigator Award to [name] (reference number: 207511/Z/17/Z)

The research costs for the LTBI treatment sub-study have been supported by an NIHR Doctoral Research Fellowship Award to [name] (reference DRF-2018-11-ST2-004).

Participant costs for extra attendances to clinic for research purposes will be met by flat rate re-imburement of £10 per extra attendance, covered by the research funding.

14. Peer and regulatory review

The study has been peer reviewed in accordance with the requirements outlined by UCL. The sponsor considers the procedure for obtaining funding from Wellcome Trust and NIHR to be of sufficient rigour and independence to be considered an adequate peer review.

15. Monitoring and auditing

The CI will ensure there are adequate quality and number of monitoring activities conducted by the study team. This will include adherence to the protocol, procedures for consenting and ensure adequate data quality. The CI will inform the sponsor should he/she have concerns which have arisen from monitoring activities, and/or if there are problems with oversight/monitoring procedures.

16. Training

The CI will review and provide assurances of the training and experience of all staff working on this study. Appropriate training records will be maintained in the study files.

17. Publication and dissemination policy

The CI will be responsible for ensuring that this study conforms to sponsor (UCL) and funder (Wellcome Trust, NIHR) policies on open access publishing (<http://www.ucl.ac.uk/library/open-access> and <https://wellcome.ac.uk/funding/managing-grant/open-access-policy>). In addition, the CI will ensure that this study will conform to ICJME policy on authorship and non-author contributors for publications (<http://www.icjme.org/recommendations/browse/roles-and-responsibilities/defining-the-role-of-authors-and-contributors.html>)

References

1. WHO | *Global tuberculosis report 2016*.
3. Rangaka, M. X. *et al.* Predictive value of interferon- γ release assays for incident active tuberculosis: a systematic review and meta-analysis. *Lancet Infect. Dis.* **12**, 45–55 (2012).
4. Pai, M. *et al.* Gamma interferon release assays for detection of Mycobacterium tuberculosis infection. *Clin. Microbiol. Rev.* **27**, 3–20 (2014).
5. Houben, R. M. G. J. & Dodd, P. J. The Global Burden of Latent Tuberculosis Infection: A Re-estimation Using Mathematical Modelling. *PLoS Med.* **13**, e1002152 (2016).

Appendix 2a: Summary of study schedule

Appendix 2b: Summary of schedule for LTBI treatment sub-study

Appendix 3: Summary of research samples tests at each study visit

Sample	Purpose	Processed by
Blood samples		
Pre-TST only	10 mL EDTA sample for DNA	DNA genotyping UCL study research laboratory
Pre-TST and all follow-up visits up to 2 years	2 mL serum	C-reactive protein NHS clinical laboratory
	3 mL Tempus RNA tube	RNA profiling UCL study research laboratory
	3 mL Quantiferon Gold Test	IGRA UCL study research laboratory
	20 mL heparinised blood	Storage of peripheral blood mononuclear cells for mechanistic studies UCL study research laboratory
LTBI treatment sub-study visits	2 mL serum	C-reactive protein NHS clinical laboratory
	3 mL Tempus RNA tube	RNA profiling UCL study research laboratory
Recall visit	Up to 120 mL heparinised blood sample	Isolation of immune cells for in vitro mechanistic studies UCL study research laboratory
Skin biopsies		
3mm punch biopsy at one TST site	RNA profiling	UCL study research laboratory
3mm punch biopsy at second TST site	RNA profiling	UCL study research laboratory

Appendix 4: Standard operating procedure for TST and biopsies

1. At time 0

- Before administration of intradermal tuberculin, take following blood samples
- Administer 2U Mantoux (Tuberculin) by intradermal injections into volar surfaces of each forearm
- Mark the injection site blebs with indelible ink

2. At 48 hours

- Measure induration and take clinical photograph at both TST sites.
- At one TST injection site, infiltrate the injection site with local anaesthetic (2% lignocaine) and wait for 5 minutes.
- Perform one 3mm punch skin biopsy at the anaesthetised site and place sample into 1 mL RNALater buffer.
- Transfer samples to research laboratory for storage- store RNA sample at -80°C

3. At 1 week

- At the second TST injection site, infiltrate the injection site with local anaesthetic (2% lignocaine) and wait for 5 minutes.
- Perform one 3mm punch skin biopsy at the anaesthetised site and place sample into 1 mL RNALater buffer.
- Transfer samples to research laboratory for storage- store RNA sample at -80°C

4. At 2 weeks

- Contact patient to ensure biopsy sites are healing well

